#### Efficacy Endpoints at Week 52 (Part B)

Efficacy endpoints at week 52 (Part B) will be analyzed descriptively at given visits for treatment received in Part B as well as by treatment group as in Part A (double-blind treatment period). No missing values will be imputed. These descriptive analyses may include statistical tests depending on the type of data in the same way as described above.

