#### Analysis Methods:

#### Primary Efficacy Analysis in Part A

The primary analysis of proportion of patients achieving a histologic response of peak esophageal intraepithelial eosinophil count  $\leq 6 \operatorname{eos/hpf} at$ 

week 16 will be analyzed using the Cochran-Mantel-Haenszel (CMH) test to assess the difference in the proportion of responders in the full analysis set (FAS), adjusting for the randomization stratification factor (baseline weight group). The randomization stratification of baseline weight group may be pooled to ensure the sufficient sample size of each stratum.

To account for use of rescue treatment, patients will be considered as non-responder after rescue treatment.

If a patient has missing value for the histological response (peak esophageal intraepithelial eosinophil count  $\leq 6 \text{ eos/hpf}$ ) at week 16, the patient will be classified as a non-responder at week 16.

Sensitivity analyses will assess alternative methods to impute missing data. The sensitivity analyses will include a tipping point analysis approach and a worst observation carried forward -Multiple Imputation (WOCF-MI) approach.

Subgroup analyses (eg, by weight) may be performed. Details will be specified in the SAP.

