#### Analysis of secondary endpoints in Part B

Efficacy data in Part B will be summarized with descriptive statistics for treatment received in Part B as well as by treatment group as in Part A (double-blind treatment period). No missing values will be imputed.

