#### 4.1.2. Secondary Endpoints

#### Secondary Efficacy Endpoints for Part A and B:

- Proportion of patients achieving peak esophageal intraepithelial eosinophil count of <15 eos/hpf at week 16
- Percent change in peak esophageal intraepithelial eosinophil count (eos/hpf) from baseline to week 16
- Absolute change in mean EoE grade score from the EoE-HSS from baseline to week 16
- Absolute change in mean EoE stage score from the EoE-HSS from baseline to week 16
- Absolute change in EoE EREFS from baseline to week 16
- Change from baseline in the type 2 inflammation transcriptional signature score at week 16
- Change from baseline to week 16 in the proportion of days with 1 or more EoE signs as measured by the Pediatric EoE Sign/Symptom Questionnaire-caregiver version (PESQ-C) (for patients aged ≥1 to <12 years)
- Number of sign-free days during the 14-day period preceding week 16 as measured by the PESQ-C (for patients aged ≥1 to <12 years)
- Change from baseline to week 16 in the proportion of total segments within a day (night, morning, afternoon, evening) with 1 or more EoE signs as measured by PESQ-C (for patients aged ≥1 to <12 years)
- Change from baseline to week 16 in the proportion of days with 1 or more EoE symptoms as measured by PESQ-P (patient version) (for patients aged  $\geq 8$  to <12 years)
- Number of symptom-free days during the 14-day period preceding week 16 as measured by the PESQ-P (patient version) (for patients aged ≥8 to <12 years)
- Change from baseline to week 16 in the proportion of total segments within a day (night, morning, afternoon, evening) with 1 or more EoE symptoms as measured by PESQ-P (for patients aged ≥8 to <12 years)
- Change in total score from baseline to week 16 as measured by the PEESSv2.0caregiver version questionnaire (for patients aged  $\geq 1$  to <12 years)
- Normalized Enrichment Scores (NES) for the relative change from baseline to week 16 in the EoE diagnostic panel (EDP) transcriptome signature
- NES for the relative change from baseline to week 16 in the type 2 inflammation transcriptome signature
- NOTE:
  - All the above primary and secondary endpoints (except for PEESSv2.0- caregiver version questionnaire) assessed at week 16 will be assessed at week 52 as secondary endpoints and summarized with descriptive statistics based on the

Regeneron Pharmaceuticals, Inc.

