# 8.3. **Rescue Treatments and Procedures**

If medically necessary (eg, for treatment of intolerable EoE symptoms), rescue medications (systemic and/or swallowed topical corticosteroids) or emergency esophageal dilation are allowed for study patients. For Parts A and B, an endoscopy with biopsy will be performed prior to the initiation of rescue therapy. Patients who undergo an endoscopy with biopsy due to the initiation of rescue therapy during Parts A or B will not undergo the subsequent scheduled endoscopy/biopsy at week 16 and/or week 52, respectively. Patients who receive rescue treatment during the double-blind period of the study will not be eligible for the extended active treatment period unless an endoscopy with biopsy is performed prior to the initiation of rescue treatment is also allowed. If rescue therapy is initiated during Part C (OLE), an endoscopy/biopsy before initiating rescue treatment is at discretion of the investigator discretion; future endoscopies/biopsies (week 100 and week 160) would still be required. If the endoscopy with biopsies cannot occur due to COVID-19 restrictions, rescue treatment should be initiated without delay and these patients will be eligible to participate in Part C.

Regeneron Pharmaceuticals, Inc.

Patients receiving rescue therapy may continue to receive study drug. They will remain blinded and will be asked to return to the clinic for all remaining study visits for the double-blind treatment period and the follow-up period, and participate in all assessments for these visits according to the Schedule of Events specified in Table 1, Table 2, Table 3, and Table 4 except for endoscopy/biopsy, as noted above. For the purpose of efficacy analyses for Part A, patients who receive rescue treatment during the study will be considered treatment failures.

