### 9.1.1. Footnotes for the Schedule of Events Tables

#### 9.1.1.1. Footnotes for Table 1

- 1. For patients without a satisfactory prior endoscopy/biopsy (eg, histological criteria were not met, or the biopsy was not performed while patient was on at least 8 weeks of PPI treatment), the screening period will be extended for up to 12 weeks (day -85) to allow for at least 8 weeks of PPI treatment prior to the screening endoscopy/biopsies. For all other patients, the screening period will be shorter, with sufficient time to allow screening assessments and laboratory test results to be available prior to the baseline endoscopy/biopsies.
- 2. The endoscopy/imaging for EoE-EREFS/biopsy procedures should be performed after all other efficacy and safety assessments.

2a. The baseline esophageal endoscopy with biopsies and the stomach and/or duodenum endoscopies with biopsies should be performed with sufficient time to allow for availability of the intraepithelial eosinophil count result from the central pathology laboratory prior to day 1. For patients without a satisfactory prior historical endoscopy/biopsy, the baseline endoscopy/biopsies must be performed after at least 8 weeks of PPI. Patients may be randomized as soon as their endoscopy/biopsy results are confirmed, and all other eligibility criteria are met.

2b. For patients who receive rescue treatment during the double-blind treatment period, the endoscopy/EoE-EREFS/biopsy procedures will be performed prior to the initiation of rescue treatment. Patients undergoing endoscopy/biopsy prior to rescue will not undergo the subsequent scheduled endoscopy/biopsy at week 16 and/or week 52.

- 3. Patients may be re-screened if they fail the screening evaluation, unless the reason for screen failure is related to histologic or clinical disease severity inclusion criteria. The baseline endoscopy with biopsy and EoE-EREFS scoring will not be repeated for rescreened patients. These results will continue to be valid baseline data. Re-screening must occur within 6 months of the screen failure.
- 4. Assessments indicated for this week 16 (end of treatment) visit should be performed for all patients. For patients who will enter extended treatment, there are additional events listed for the week 16 visit in Table 2.
- 5. Patients and/or caregivers will be trained on administration of study drug.

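### Week-52 responder rates do not carry over the week-16 rescue-as-failure rule or say how patients without a week-52 biopsy count, and Section 8.3 conflicts with Table 2 footnote 7a on the week-52 biopsy after Part A rescue

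*Protocol*

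**What the plan says.** **Endpoints.** Under the NOTE in Section 4.1.2, the primary and secondary endpoints, apart from the PEESS questionnaire, "assessed at week 16 will be assessed at week 52 as secondary endpoints and summarized with descriptive statistics". This includes the two responder proportions, ≤6 and <15 eos/hpf.

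**Rescue and missing data at week 16.** The synopsis, under the Part A primary analysis, states: "To account for use of rescue treatment, patients will be considered as non-responder after rescue treatment". Section 8.3 gives the scope: "For the purpose of efficacy analyses for Part A, patients who receive rescue treatment during the study will be considered treatment failures". The estimand table in Section 11.4.3.1 applies a composite strategy to corticosteroid rescue and counts a missing week-16 value as non-response.

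**Week 52.** Section 11.4.3.2 (Part B) says "No missing values will be imputed. These descriptive analyses may include statistical tests depending on the type of data". The synopsis paragraph on Part B repeats "No missing values will be imputed". Neither mentions rescue.

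**Analysis set.** Section 11.3.3 and the synopsis define the Part B and C set as members of the Part A safety set with at least one dose of Part B or Part C drug.

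**Biopsies after rescue.** Section 8.3: patients biopsied because of rescue "during Parts A or B will not undergo the subsequent scheduled endoscopy/biopsy at week 16 and/or week 52, respectively". After rescue in Part C, "future endoscopies/biopsies (week 100 and week 160) would still be required". Table 1 footnote 2b: "Patients undergoing endoscopy/biopsy prior to rescue will not undergo the subsequent scheduled endoscopy/biopsy at week 16 and/or week 52". Table 2 footnote 7a says such patients skip the scheduled biopsies at both weeks 16 and 52. Table 3 footnote 4a extends the skip to any later biopsy, with weeks 100 and 160 named.

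**The concern.** Long-term efficacy is a secondary objective, and readers will set the week-52 rates beside the week-16 rates. A child who needs rescue in Part B is biopsied beforehand and then has no scheduled week-52 biopsy. The value is missing because the child needed rescue. If such children drop out of the week-52 proportion, a failure at week 16 becomes an exclusion at week 52. Part of any rise over time then comes from the change of rule, and a group with more rescue looks better. Section 11.4.3.2 displays week 52 by group and allows tests, so comparisons between groups are exposed as well as the time course.

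The biopsy wording matters for a different reason. If sites read the passages differently, some children rescued in Part A will have a week-52 biopsy and others will not. An analysis plan cannot recover a biopsy that was not taken.

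**Working it through.** **Step 1. Does any text carry the week-16 rescue rule to week 52?**
- Section 8.3 names Part A as the scope.
- The estimand table in Section 11.4.3.1 has a note applying the composite strategy to rescue at any time in the study. The note sits inside the row for the week-16 primary endpoint, so it does not define a week-52 rule.
- The sentence on tests in Section 11.4.3.2 (Part B) ends by pointing back to the methods above. Grammatically this concerns the tests. It cannot import the missing-as-non-responder rule, because the sentence before it bars imputation.

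None of the three clearly carries the rule over.

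**Step 2. Who counts in the rate?** One Part B dose is enough for membership of the set in Section 11.3.3, so a child rescued during Part B after such a dose belongs to it. The text does not say whether a member with no week-52 biopsy is counted. Three readings are open: observed cases only, the whole set as denominator, or the pre-rescue biopsy used as the week-52 value.

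**Step 3. Size.** The protocol gives no figure to reproduce here and no rescue rate. Inputs:
- N = 30 per group (Section 11.2), assumed all to enter Part B.
- x = 12 responders, from the planning rate of 40.7%: 0.407 × 30 = 12.2, taken as 12.
- m = number rescued in Part B without a week-52 biopsy: 0, 1 or 3, with 6 as a wider case. All are assumptions, and rescued children are taken not to be responders.

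Observed-case rate = x / (N − m). Whole-set rate = x / N.

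| m (assumed) | Observed cases | Whole set | Shift |
|---|---|---|---|
| 0 | 12/30 = 40.0% | 12/30 = 40.0% | 0.0 |
| 1 | 12/29 = 41.4% | 12/30 = 40.0% | +1.4 |
| 3 | 12/27 = 44.4% | 12/30 = 40.0% | +4.4 |
| 6 | 12/24 = 50.0% | 12/30 = 40.0% | +10.0 |

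Two groups that both have 12 of 30 with rescue counted as failure, one with 0 rescued and one with 3, would differ by 44.4 − 40.0 = 4.4 points on observed cases, in favour of the group with more rescue. If pre-rescue biopsies are used at week 52 and are above the threshold, the rate is again 12/30.

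**Step 4. Biopsies after rescue.** Section 7.2.2.2 criterion 3 and Section 8.3 both allow a child rescued in Part A into Part B if biopsied before rescue. For that child:
- Section 8.3 pairs Part A with week 16 and Part B with week 52, so the week-52 biopsy remains.
- Table 2 footnote 7a removes weeks 16 and 52 together, so it does not.
- Table 1 footnote 2b is close to Section 8.3 but lacks the word that makes the pairing. It can be read either way.
- Table 3 footnote 4a would remove weeks 100 and 160, which Section 8.3 keeps after Part C rescue. The footnote is marked only on the early-termination columns, so it may concern only patients who are leaving.

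**The case against.** **Counting rules for a descriptive table belong in the SAP.** Section 11 calls itself the basis for the SAP, and the SAP is not at hand. This has force for fine detail. But the week-52 text does not defer to the SAP, whereas the text on subgroups and on the testing hierarchy does. It fixes a no-imputation rule, and Section 8.3 fixes the Part A scope. Those two statements create the gap.

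**A denominator is stated.** A reader might infer that the protocol gives none at all. It does not support that: Section 11.3.3 and the synopsis define the set. Only the treatment of members without a biopsy is open.

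**The week-52 rates are not shown to be biased.** This stands. The inflation needs the observed-case reading, no use of the pre-rescue biopsy and at least one rescued child. Counting rescue as failure is not imputation, so the present text does not forbid it either.

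**The footnotes can be harmonised.** Footnote 7a is attached to both the week-16 and week-52 cells of Table 2 and could be read cell by cell. A reader might also infer four contradictory schedules, which is too strong given how loose 2b is and where 4a is marked. What stands is that 7a, as worded, removes a biopsy that Section 8.3 keeps.

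**It is late.** In this version Part A has been reported and some patients had already completed their end-of-study visit. For them a settled biopsy rule comes too late; how many others are affected is unknown. The analysis rule can still be stated.

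**Conclusion.** The point holds in limited form. The rescue-as-failure rule is tied to Part A and is not clearly carried to the repeated responder endpoints at week 52. The counting of set members without a week-52 biopsy is also left open. On the observed-case reading the week-52 rate is more favourable than the week-16 rule would give. The direction is clear if rescued children are not responders, but the size cannot be taken from the documents: 1.4 points for 1 rescued and 4.4 points for 3 rescued, with 12 responders of 30, and zero if nobody is rescued or the whole set is the denominator.

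Section 8.3 and Table 2 footnote 7a conflict on the week-52 biopsy after Part A rescue. Table 1 footnote 2b is ambiguous, and Table 3 footnote 4a is a weaker conflict of general wording.

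A reader might infer a threat to the trial's main conclusion. There is none: week 52 is a descriptive secondary analysis outside the testing hierarchy, and the primary analysis and type I error are unaffected. The change is worth making, with medium confidence.

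**What to change.** In Section 11.4.3.2 (Part B) and the matching synopsis paragraph, for the ≤6 and <15 eos/hpf proportions at week 52:
1. Count patients rescued before week 52 as non-responders in the denominator, and state explicitly how rescue in Part A is treated.
2. Report the observed-case rate alongside, with the number missing for other reasons. Leaving those patients out with their count shown keeps the no-imputation rule.
3. Say whether a pre-rescue biopsy is used as the week-52 value.

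Separately, reconcile Section 8.3, Table 1 footnote 2b, Table 2 footnote 7a and Table 3 footnote 4a on which scheduled biopsies follow rescue. This review does not choose the schedule.

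The cost is two or three sentences, an extra line in the week-52 table and corrected footnotes. Alpha, sample size and the primary analysis do not change.

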#### Efficacy Endpoints (Part C)

Efficacy data in Part C will be summarized with descriptive statistics for treatment received in Part C as well as by treatment group as in Part A (double-blind treatment period) and Part B (extended active treatment period). No missing values will be imputed.

#### **11.4.4.** Control of Multiplicity

For multiplicity adjustment, a hierarchical procedure will be used to control the overall Type-1 error rate at 0.05 for the primary endpoint and the selected secondary efficacy endpoints for each dupilumab dose regimen versus placebo in Part A only. Each hypothesis will be formally tested only if the preceding one is significant at the 2-sided 0.05 significance level. The primary endpoint will be tested for the higher exposure dupilumab group first and then for the lower exposure dupilumab group. The hierarchical order of the secondary endpoints will be specified in the SAP.

As Part B and C data will be summarized using descriptive statistics, there is no multiplicity issue.

#### 11.4.5. Safety Analysis

Safety analysis will be based on the SAF in the respective study part. This includes reported TEAEs and other safety data (ie, clinical laboratory evaluations and vital signs). A descriptive summary of safety results will be presented for each study part by treatment that patients receive in respective part as below:

• Part A: placebo, lower dupilumab exposure group, higher dupilumab exposure group and combine dupilumab group

• Part B: lower dupilumab exposure group, higher dupilumab exposure group and total

Pooled Part A and Part B may be presented and details will be specified in SAP.

• Part C: higher dupilumab exposure group

#### 11.4.5.1. Adverse Events

#### **Definitions**

For safety variables, 2 observation periods are defined:

- The pretreatment period is defined as the time from signing the ICF to before the first dose of study drug.
- The treatment-emergent period is defined as the day from first dose of study drug to end of study. The treatment-emergent period includes the double-blind treatment period, extended active treatment period, and open-label extension period (up to 160 weeks in total) and the 12-week follow-up period.
  - Treatment period: date of the first dose of study drug to week 160 visit date for those patients who completed the week 160 visit with available visit date; or date of the first dose of study drug to study day 1121 (study day 1 being the first dose date) or the date of patient last contact, whichever is earlier, for those patients who did not complete week 160 visit or had missing week 160 visit date
  - Follow-up period: date after the end of treatment period to end of study

Treatment-emergent adverse events are defined as those that are not present at baseline or represent the exacerbation of a pre-existing condition during the treatment-emergent period.

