# CONFIDENTIAL

	Patients are required to have a documented diagnosis of EoE that may be established either by a prior historical biopsy, as demonstrated by intraepithelial eosinophilic infiltration (peak eosinophils/high power field $\geq 15 \text{ eos/hpf}$ ) (400×) from at least 1 esophageal region and performed after at least 8 weeks of treatment with an approved proton pump inhibitor (PPI) regimen, or by biopsies performed after approximately 8 weeks of PPI treatment initiated prior to screening or during the screening period, which demonstrates $\geq 15 \text{ eos/hpf}$ ) (400×) from at least 2 of the 3 esophageal regions (proximal, mid, and distal). Patients who are on PPIs during the screening period to rule out EoE disease management with this treatment, and are eligible to enroll in the study, have the choice either to remain on the PPI regimen during the entire study or stop the PPI regimen prior to baseline (vicit 3); they then must remain off of
	PPIs during the entire study. Biopsies will be obtained by endoscopy at screening visit 2, the week 16 visit, the week 52 visit, the week 100 visit, the week 160 visit, or immediately prior to start of rescue medication or procedures (only applies to rescue medication and/or procedures that occur before the week 52 visit). A total of at least 9 mucosal pinch biopsies will be collected at each time point from 3 esophageal regions: 3 proximal, 3 mid, and 3 distal. Two samples from each region will be used for histology (needed for study inclusion criteria, as well as endpoint assessment) and the other for RNA extraction.
	Patients may receive concomitant medications (except for prohibited medications specified in the protocol body) as needed, at the discretion of the investigator, while continuing study treatment. Frequency of use and type of product will be documented.
	Efficacy, safety, laboratory assessments, and samples for assay of concentration of functional dupilumab in serum and potential anti-drug antibody (ADA) response to dupilumab, as well as research samples, will be performed or collected at specified time points throughout the study according to Schedule of Events specified in the protocol body.
Study Duration	The duration of the study for a patient is up to 172 weeks, excluding the screening period.

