- 5. All females post-menarche must have monthly pregnancy testing during Part C (Table 4). In case of a positive urine test, the study treatment will be withheld and a serum pregnancy test to confirm the pregnancy should be performed as soon as possible. A confirmed pregnancy will lead to study drug discontinuation in all cases.
- 6. Urinalysis is only required for patients aged  $\geq 6$  years.
- 7. Patients who have completed their end of study visit (Visit 18 in previous protocol versions) prior to entering the open-label extension period must complete the procedures indicated for the Re-Entry Visit (Table 2) and are eligible for re-entry to the study for the open-label extension period and safety follow-up periods only. The Re-Entry Visit for eligible re-entry patients may be combined with the week 52 Visit procedures for Part C (Table 4).
- The Pediatric Eosinophilic Esophagitis Symptom Score (PEESS) version 2.0 will be completed by caregivers of patients ≥1 to <12 years of age (determined at the time of screening visit 1).

Regeneron Pharmaceuticals, Inc.

- 9. These procedures are required for re-entry patients only.
- 10. EoE-EREFS imaging will be analyzed and scored by a central reading center. Minor esophageal features will be assessed by the investigator.
- 11. For the phone visits, patients are not required to come to the clinic. Patients may have study drug shipped to them and administered at home by their parents and/or caregivers; however, patients and their parents/caregiver have the option to come to the clinic and have study drug administered by site personnel if they prefer to do so. Phone contacts at any time during Part C are encouraged to ensure compliance and safety of study drug dosing.
- 12. Blood samples for dupilumab concentration measurement will be collected before the administration of study drug. The PK sample collected may be used for dupilumab ADA analysis based on the overall clinical presentation at that time. In the event of suspected SAEs, such as anaphylaxis or hypersensitivity, additional blood samples may be collected at or near the event for PK and ADA assessments.
- 13. The End of Study (EOS) visit may occur twice for Re-Entry patients.
- 14. Weight-based dosing should be adjusted based on the patient's weight at specified in-clinic visits.

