#### 9.1.4. **Re-Entry Visit**

Patients who have completed their end of study visit prior to entering the open-label extension period are eligible for re-entry to the study for the open-label extension period. The following study procedures are required at a Re-Entry Visit:

- Part C re-entry criteria (Section 7.2.2.2)
- Informed consent
- Updates for all relevant medical history and prior and concomitant medications/procedures
- Physical Examination
- Age, weight, height (length for patients <2 years of age)

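### The treatment and follow-up periods for adverse events run on one clock capped at study day 1121, which mislabels Part C time for children who enter Part C after a break.

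*Protocol*

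**What the plan says.** Protocol Section 11.4.5.1 (Adverse Events, Definitions) sets a single interval: "The treatment-emergent period is defined as the day from first dose of study drug to end of study". It describes the content of that interval as the double-blind, extended active and "open-label extension period (up to 160 weeks in total) and the 12-week follow-up period". The treatment period inside it has two rules:

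- Children with a week-160 visit: "date of the first dose of study drug to week 160 visit date for those patients who completed the week 160 visit".
- Children without that visit, or without its date: first dose to "study day 1121 (study day 1 being the first dose date) or the date of patient last contact, whichever is earlier".

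Everything after the treatment period, up to end of study, is follow-up. Re-entry is not mentioned.

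The same protocol provides for breaks before Part C:

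- Section 6.1 lets children who completed EOS before Amendment 4 be re-evaluated at a Re-Entry visit for Part C. Children still in the safety follow-up may enter Part C directly, without an EOS visit.
- Table 4, footnote 7, allows the Re-Entry visit to be combined with the week-52 procedures, so nominal week 52 is set at re-entry. Footnote 13 adds: "The End of Study (EOS) visit may occur twice for Re-Entry patients".
- Section 9.1.4 asks for new consent and "Updates for all relevant medical history and prior and concomitant medications/procedures" at re-entry.

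The Synopsis states: "The duration of the study for a patient is up to 172 weeks, excluding the screening period".

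**The concern.** The day-1121 cap counts calendar days from the first dose in Part A. Nominal Part C visits for a re-entry child count from re-entry. The two clocks agree only if nothing separates Part B from Part C. When something does, the treatment period of a week-160 completer contains time with no study drug and, in part, outside the study. For a child without a week-160 visit, the cap can fall while dosing continues, and later on-drug events are then assigned to follow-up.

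At stake is the assignment of long-term adverse events to the right period. Amendment 4 was written mainly to add long-term safety data. Section 4.1.2 lists incidence of TEAEs, SAEs and AESIs during the 108-week open-label extension as endpoints, and Section 11.4.5 reports safety by study part. Section 11.4.5.1 gives no event window for Part C to match. The Synopsis duration has the same origin, since it too adds up an unbroken sequence.

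**Working it through.** **Inputs.** Part A 16 weeks, Part B 36, Part C 108, follow-up 12 (Section 6.1). Last Part B dosing at week 50 (Table 2, footnote 4a). Gap g, in weeks from first EOS to re-entry, is not in the protocol. It is an assumption, shown at 0, 26 and 52.

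**The plan's own figure.** Study day = 7 × week + 1. Total treatment is 16 + 36 + 108 = 160 weeks, and 7 × 160 + 1 = 1121. This reproduces the cap exactly and shows that it presumes no break.

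**Re-entry child.**

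- Week 52 is day 365. First EOS is about 12 weeks later, day 365 + 84 = 449 (week 64).
- Re-entry is on day 449 + 7g.
- The nominal week-160 visit is 108 weeks later: day 449 + 7g + 756 = 1205 + 7g.
- Overrun past the cap is 1205 + 7g − 1121 = 84 + 7g days, or 12 + g weeks.
- Nominal week on day 1121 is 160 − (12 + g) = 148 − g.
- Part C days inside the cap are 756 − (84 + 7g) = 672 − 7g.

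**Completers.** Follow-up plus off-study gap inside the treatment period is also 84 + 7g days, out of 1205 + 7g. Counting from the last Part B dose at week 50 instead of week 52 adds 14 days.

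| g (weeks) | Week-160 visit, study day | Completer: follow-up + gap counted as treatment | No week-160 visit: nominal week at day 1121 | Part C dosing that can fall in follow-up | Part C days inside cap, of 756 |
|---|---|---|---|---|---|
| 0 | 1205 | 84 days (84/1205 = 7%) | 148 | up to 12 weeks | 672 (89%) |
| 26 | 1387 | 266 days (266/1387 = 19%) | 122 | up to 38 weeks | 490 (65%) |
| 52 | 1569 | 448 days (448/1569 = 29%) | 96 | up to 64 weeks | 308 (41%) |

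The last two columns are bounds. They apply to a child without a week-160 visit or date who is still being dosed after day 1121. Lacking that visit is partly by design: Part C may end early on commercial availability (Section 6.1) or on reaching the age and weight criteria (Section 8.1).

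**Entry from safety follow-up without EOS.** If Part C starts f weeks after week 52, with f from 0 to 12, the overrun is 7f days: 0 to 84 days, at most 12 weeks.

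**Duration.** The stated maximum is 16 + 36 + 108 + 12 = 172 weeks. A re-entry child has two follow-up periods: 52 + 12 + 108 + 12 = 184 in-study weeks, not counting g.

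**The case against.** The strongest reply is that little reported output changes, and much of it stands.

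- The cap divides treatment from follow-up, and both lie inside the treatment-emergent period. An event after day 1121 is still a TEAE.
- Section 11.4.5.3 computes exposure separately for each part, so the gap does not enter it. Section 11.4.5.1 plans counts and percentages, with no person-time rates for the gap to dilute.
- Section 11 is described as the basis for the SAP, and part-specific event windows are often set there.

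Two stronger readings are tempting and should not be drawn.

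A reader might infer that, because EOS can occur twice, the window closes at the first EOS and no Part C event of a re-entry child is treatment-emergent. The next sentence of Section 11.4.5.1 expressly includes the open-label extension and its follow-up, and Section 6.1.1 defines end of study by the last patient. Neither fits that reading.

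A reader might also infer that any condition arising in the gap becomes a TEAE because it was absent at the original baseline. Re-entry requires new consent and a medical-history update. Table 2 has no adverse-event entry at that visit, and Section 10.1.1 sends conditions that predate consent to medical history. Gap conditions would mostly be recorded as history.

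What the reply does not remove is that Section 11.4.5.1 states a complete rule with a fixed day. Followed as written, it assigns some on-drug Part C time to follow-up, and some off-drug time to treatment. The open-label endpoints need a period assignment, and this is the only one the protocol supplies.

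**Conclusion.** The definition does not fit the protocol's own re-entry rules and should be corrected. For re-entry completers, 12 + g weeks of follow-up and off-study time count as treatment. For re-entry children without a week-160 visit, up to 12 + g weeks of Part C dosing count as follow-up. Children entering from the safety follow-up are affected by up to 12 weeks. The 172-week maximum understates in-study time for re-entry children by 184 − 172 = 12 weeks.

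The effect is misclassification by period, and no event loses its treatment-emergent status. Part A and the efficacy analyses do not depend on these definitions. The size rests on a first EOS at about week 64 and on g, which is assumed. Neither g nor the number of children concerned is in the protocol, so the overall effect on the Part C safety tables cannot be stated.

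**What to change.** In Section 11.4.5.1:

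- Define the Part C treatment period from the first Part C dose to the week-160 visit. For children without that visit or its date, end it at the earlier of last contact and day 757 counted from the first Part C dose as day 1 (108 × 7 + 1 = 757). This also covers children entering from the safety follow-up.
- Exclude the interval between first EOS and re-entry from the treatment-emergent period.
- State that the re-entry visit is the baseline for Part C adverse events in re-entry children, and that their second EOS closes the window.

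In the Synopsis, give the maximum in-study duration for re-entry children as up to 184 weeks, excluding the off-study gap.

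The cost is wording in two places and a derived Part C start date for each child who enters Part C after a break. No new data are needed.
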